7.3 LOST TO FOLLOW-UP

Since the study primary outcome is retention, study staff will not contact caregivers or ALHIV who miss their appointments for longitudinal survey data collection. However, we will contact stakeholders and HCW as needed to schedule study related activities.

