Procedures to minimize psychological risks: All participants will be assured that their participation is voluntary and that they may withdraw from the study at any time. Kenyan study personnel experienced in research with adolescents will be available for questions when participants take the surveys. While there is a risk of discomfort related to answering sensitive questions about sexual behavior, mental health, and stigma on the surveys, these questions are similar to what would be asked as part of routine HIV care for adolescents. Survey participants will be informed that they can skip any question or stop the interview at any time. Any participant who reports emotional distress, exposure to violence, or other threat will be offered support or referral to additional services, as appropriate, according to standard operating procedures. Some younger adolescents receiving HIV care and taking ART (which may be called 'medicine' and not HIV medicine) may not yet know their HIV status, because the caregiver is not ready for the child to learn this information. The ALHIV surveys will not include specific mention of HIV or ART unless a participant reports knowledge of their own HIV status on a screening question. This approach will minimize the possibility of involuntary disclosure to an ALHIV and maximize representative enrollment.

Procedures to minimize other risks: Study staff will be trained to take all precautions to ensure confidentiality of participation and data collected and will have standardized operating procedures (SOPs) to follow to minimize the risks of a participant's loss of confidentiality. Risk of breach of confidentiality of study data is low, as all patient data collected will not include names and will be located on a password protected secure study server. ALHIV participants will be assured that their sensitive information will not be shared with anyone outside the study team, including a parent, caregiver, or partner who may be present. Study staff will be trained in the importance of confidentiality during training prior to study implementation. The community-driven process of adaptation and optimization of the intervention to local context will ensure that the intervention is culturally sensitive before implementation in the pilot and RCT. All HCW participants will be assured that their participation will not affect their employment status.

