behavioral surveys at enrollment and every 6 months thereafter. Clinic staff members will refer to the study team a purposeful sample of caregivers of adolescents coming in for routine clinic visits. A large number of adolescents come to clinic alone; the study will only recruit caregivers who accompany adolescents. Caregivers who meet eligibility criteria will be invited to enroll and complete caregiver surveys at enrollment and at 12 months.

HCW surveys

HCW in participating sites working in the ALHIV clinic will be invited to participate in health service and implementation surveys. A script outlining talking points, purpose and scope of work will be used for recruitment. Written informed consent for participation will be collected from all participants prior to study activities.

Participant incentives

The study will provide reimbursement for transportation costs, accommodation and meals during the workshop and provide a per-diem allowance equal to current rates used by organizations or facilities where the HCWs work.

Adolescents and caregivers who participate in surveys will be reimbursed KSH 200 (\$2.00 USD). HCW attending study related meetings and completing surveys will be reimbursed KSH 1000 (~10USD).

Population justification

This study will be conducted in ALHIV age 10-24 years old, who have a high risk of mortality, and require innovative client-centered strategies to improve retention, adherence, and viral suppression. The study will be conducted in Kenya, where 140,000 adolescents (ages 10-19) have HIV, and HIV is among the leading causes of mortality in this age group.

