Program records: We will abstract ALHIV medical record data at baseline and regular intervals throughout the study. Data from all adolescents with at least 1 clinic record within the 12-month period prior to the first data abstraction date will be included. Data will be abstracted at the facility or at the office of the technical partner that supports the EMR system at the facility. The EMR system captures data on client anthropometric measures, demographics, HIV testing history, family members, clinical history, ART adherence data, laboratory data, CD4 count, transfers, and discontinuations. Routine viral load testing (done 6 months after ART initiation, then annually) will be abstracted from the EMR, if available, or NASCOP's laboratory database. If EMR data is unavailable, paper medical records will be abstracted using mobile REDCap which enables automatic upload of data to a secure, password-protected study server.

Adolescent behavioral surveys: Adolescent surveys will include questions on socio-demographics, health care use, stigma, sexual behavior, psychosocial support, mental health, personal health knowledge, HIV disclosure and medication adherence. Surveys will be administered every 6 months either in-person or over phone by a trained study staff. Survey visits will coincide with clinic visits as much as possible.

Caregiver behavioral surveys: Caregiver surveys will include questions on socio-demographics and family, caregiver roles, HIV disclosure, HIV care experience, disclosure, social support, mental health, HIV testing and awareness, personal health and HIV experience, HIV stigma, ART knowledge and adherence. Surveys will be administered every 12 months either in-person or over phone by a trained study staff. Survey visits will coincide with clinic visits as much as possible.

Data on health services and implementation outcomes will be collected as previously described (see section 6.2).

To track implementation, the following surveys will be conducted:

Facility surveys: Facility managers will complete baseline and annual facility surveys to understand baseline resource capacity to implement future interventions and modifiable and non-modifiable health system factors. Variables will include availability of youth-friendly services, management and referral systems, and differentiated care services available.

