HCW implementation logs: These will be collected weekly and combined with information collected in annual HCW surveys to understand intervention and implementation processes in real time and service efficiency outcomes. We will specifically evaluate the percent of HCWs using the intervention, percent of adolescents in each step, percent of adolescents assigned to correct step, and percent of adolescents ‘adherent’ to services in each step. We will also collect basic information on numbers of adolescents attending clinic each week, and the number exposed to the intervention. In control sites, we will collect information on classification of adolescents as stable/unstable and offer for differentiated services.

ALHIV and caregiver satisfaction surveys: Surveys will be given to a random sample of adolescents and caregivers in intervention sites at the end of the study to evaluate satisfaction with their care.

ALHIV FGDs/IDIs: We will conduct FGDs/IDIs with adolescents in intervention sites at the end of the intervention period to determine acceptability, feasibility and satisfaction with the intervention. FGD/IDI participants will be purposively selected from adolescents in intervention clinics. We will conduct FGDs/IDIs with up to 50 people per facility.

The table below summarizes study outcomes and definitions

Summary of outcomes and definitions

Aims	Outcome type	Outcome	Definition
Aim 1	Primary	Final optimized DiSC intervention	Modified DiSC intervention with input from workshop and pilot phase
	Secondary	DiSC intervention feasibility	Suitability for everyday use and practicality

Adapted from NIH Behavioral and Social Intervention Clinical Trial Protocol Template v3.0 - 20180827

		DiSC intervention acceptability	HCW satisfaction with the intervention
		DiSC intervention adaptation and fidelity	The degree with which the intervention is modified and implemented as planned
Aim 2	Primary	Retention in care	>30 days late for a scheduled visit at 6-month intervals
	Secondary	ART adherence	Proportion of days on ART based on last dispense date
		Viral suppression	<50 copies per milliliter and a second analysis using greater than lower limit of detection
		Co-factors of retention and viral suppression	School drop-out, relationships, depressive symptoms, substance use, social support, and satisfaction with care
		ALHIV self-efficacy	Self-efficacy scales from standard questionnaires
		Health service efficiency	Client wait time

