9.4.3 ANALYSIS OF THE SECONDARY ENDPOINT(S)

Intervention effectiveness on secondary outcomes, including and the proportion virally suppressed at 6 and 12 months, proportion with >80% adherence since last refill, the proportion retained at 18 and 24 months, and proportion virally suppressed at 18 and 24 months, will be evaluated in separate regression models. Mediation analyses to understand mechanisms of intervention effectiveness will include whether intervention effectiveness is partially explained by ALHIV satisfaction and self-efficacy.

Intervention impact on systems efficiencies will be evaluated in regression models comparing intervention and control clinics on service outcomes including median client wait time. We will include selected costing indicators at all sites in consultation with the UW CFAR Health Economic Impact Study Team for future cost-modeling, although a complete cost-effectiveness analysis is beyond the scope of this application.

Implementation outcomes and health system outcomes will be evaluated using standard qualitative and quantitative analysis methods, corresponding to the type of data collected to measure each implementation outcome. The majority of implementation surveys will be evaluated using Likert scales, and data will be summarized using basic descriptive statistics. Qualitative data will be analyzed using thematic analysis approaches that account for the use of implementation frameworks (CFIR, FRAME). Themes will be organized based on selected frameworks. Adaptation of the intervention will include measuring micro-changes tested and evaluation of the results of these changes.

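### Follow-up survey outcomes will be missing mainly among adolescents not retained, and unequally by arm if DiSC works, with no analysis planned for it

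*Protocol*

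**What the plan says.** Protocol 7.3 gives the rule and its reason: "Since the study primary outcome is retention", "study staff will not contact caregivers or ALHIV who miss their appointments for longitudinal survey data collection". No end date is attached.

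The cohort completes "behavioral surveys at enrollment and every 6 months thereafter" (protocol 5.5). Protocol 8.1 adds "Surveys will be administered every 6 months either in-person or over phone by a trained study staff" and "Survey visits will coincide with clinic visits as much as possible". The Schedule of Activities gives months 6 and 12 a window of plus or minus 2 months. Protocol 7.2 lists loss to follow-up as a ground for discontinuation and lets discontinued participants be replaced.

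Survey measures serve as effectiveness outcomes in the protocol:
- self-efficacy is a secondary endpoint (synopsis, section 3, and the outcomes table in 8.1);
- section 4.1 hypothesises better psychosocial support, mental health and self-efficacy under DiSC;
- Table 3b plans 1500 adolescent surveys per arm for mediators and secondary outcomes;
- section 9.4.3 plans a mediation analysis of "whether intervention effectiveness is partially explained by ALHIV satisfaction and self-efficacy".

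The SAP is narrower. Its primary and secondary outcomes (2.1, Table 1) come from the EMR, the NASCOP database or paper records, and adherence self-efficacy appears only as a baseline characteristic. SAP Section 4 discusses missing EMR and viral load data and rules out formal imputation. It does not mention missing surveys.

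**The concern.** Whether an adolescent answers the month-6 or month-12 survey depends on whether he or she is still attending. Attendance is a post-randomisation variable, and DiSC is designed to change it. If DiSC works, its survey sample includes adolescents who would have dropped out under standard care, while their counterparts in control clinics go unsurveyed. Randomisation no longer guarantees that the two groups of responders are comparable, and the imbalance grows with the retention effect. The mediation analysis has a related problem: the mediator is missing preferentially where retention failed.

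The protocol gives some reason to expect a direction. Its background (2.2, B3) names poor mental health, stigma, substance use and lack of support as risk factors for poor adherence and retention. Adolescents kept in care only by DiSC may therefore score worse, which would make DiSC look worse on these measures than it is.

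**Working it through.** **The plan's own figures.** The documents give no figure for survey completeness. The design retention rates come from the sample-size sections. Protocol Table 3a reproduces with the Hayes-Bennett formula, c = 1 + (1.96 + 0.84)² × [p0(1-p0)/m + p1(1-p1)/m + k²(p0² + p1²)] / (p0 - p1)², with k = 0.15 and p0 = 75%. For p1 = 90%, 92% and 93% it gives 12.74, 10.32 and 9.39 clinics per arm at m = 100 (stated 13, 11, 10), and 13.71, 11.03 and 10.00 at m = 50 (stated 14, 12, 10).

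**Precision is not the problem.** For an outcome of 75% versus 92% at 50 per clinic, the formula gives 11.03 clinics per arm. With only 37.5 and 46.5 surveyed per clinic (75% and 93% of 50), it gives 11.40.

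**Missing surveys.** Inputs: 75% in control and 89% under DiSC (SAP 2.2.1), and 1500 surveys per arm (protocol Table 3b). Assume that no non-retained adolescent is surveyed. Then 25% of controls (375) and 11% of intervention adolescents (1500 - 1335 = 165) lack the survey.

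**Share without a counterpart.** Assume also that DiSC loses nobody who would have stayed under standard care. The surveyed intervention group is then 75 points who would be retained either way plus 14 points retained because of DiSC. The share with no surveyed control counterpart is (p1 - p0)/p1 = 0.14/0.89 = 15.7%.

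**Apparent effect under a true null.** Shift = -gap × (p1 - p0)/p1, where the gap is how much lower the extra retained adolescents score. The documents do not give it, so it is assumed.
- Gap 0.3 SD: -0.3 × 0.157 = -0.047 SD.
- Gap 0.5 SD: -0.5 × 0.157 = -0.079 SD.
- Gap 0.8 SD: -0.8 × 0.157 = -0.126 SD.
- Binary, 70% versus 45% with high self-efficacy: (0.75 × 0.70 + 0.14 × 0.45)/0.89 - 0.70 = 0.661 - 0.700 = -3.9 points.

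**Other retention rates in the documents.**

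| Control, DiSC | Missing | No counterpart | 0.3 SD gap | 0.8 SD gap | 25-point gap |
|---|---|---|---|---|---|
| 75%, 85% | 25% vs 15% | 11.8% | -0.04 SD | -0.09 SD | -2.9 points |
| 75%, 89% | 25% vs 11% | 15.7% | -0.05 SD | -0.13 SD | -3.9 points |
| 75%, 93% | 25% vs 7% | 19.4% | -0.06 SD | -0.15 SD | -4.8 points |

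**If some of the non-retained are surveyed.** Take 75% versus 89%, the 70%/45% case, and half of the non-retained surveyed in both arms. Control: (0.525 + 0.125 × 0.45)/0.875 = 66.4%. DiSC: (0.588 + 0.055 × 0.45)/0.945 = 64.8%. The shift falls to -1.6 points.

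**How wide bounds would be.** In the same example with nobody reached, trimming the 14 extra points from the intervention responders bounds the prevalence among the always-retained between (0.588 - 0.14)/0.75 = 59.7% and 0.588/0.75 = 78.4%. Against 70% in control, that is -10.3 to +8.4 points. Bounds alone would be inconclusive, which is why weighting is also needed.

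**The case against.** The no-contact rule is deliberate and sound: tracing by study staff could itself bring adolescents back to care and contaminate the primary outcome. That stands, and nothing here argues against the rule.

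Several stronger readings are tempting, and the documents do not support them.
- *Survey outcomes exist only for those retained.* Enrollment surveys cover the whole cohort. An adolescent who misses a visit and returns can be surveyed within the 2-month windows. Protocol 8.1 permits phone surveys and ties them to clinic visits only as far as possible.
- *The comparison is conditioned on the primary outcome.* The protocol outcome is ">30 days late for a scheduled visit at 6-month intervals", and the SAP analyses missed visits as repeated measures. The selection is closer to non-return to care, a SAP secondary outcome.
- *A successful DiSC would look neutral or harmful on its secondary outcomes.* The SAP's secondary outcomes do not come from surveys. For the protocol's survey outcomes, the illustrated shifts of about 3 to 5 points are well below the 17-point difference assumed detectable in the cohort (protocol 9.2). A true effect of that size would shrink, not reverse.
- *HIV-specific items are selected differently by arm.* Protocol 2.3.3 says "The ALHIV surveys will not include specific mention of HIV or ART unless a participant reports knowledge of their own HIV status", but nothing shows that status knowledge will change differently between arms.
- *Non-attenders could be phoned once the 12-month window closes.* The protocol synopsis and 9.4.3 keep retention at 18 and 24 months as endpoints, so calls at months 13 to 14 would contaminate those. They would also mean changing 7.3 and probably ethics review.

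The objection leaves one gap: neither document says how follow-up survey data missing through non-retention will be analysed.

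**Conclusion.** The point holds as an analysis gap. Follow-up survey data will be missing preferentially among adolescents not retained, and differentially by arm if DiSC improves retention. It affects the between-arm survey comparisons and the mediation analysis in protocol 8.1 and 9.4.3, and leaves the trial's main conclusion on retention untouched.

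At 75% versus 89%, the upper case is 25% versus 11% missing, 15.7% of intervention responders without a counterpart, and a spurious -0.05 to -0.13 SD or -3.9 points. These figures assume that no non-retained adolescent is surveyed, that DiSC drives nobody out of care, and score gaps that the documents do not supply. The 89% is a detectable difference in the SAP, not a forecast. The direction is plausible from the protocol's background but is not established for self-efficacy.

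**What to change.** Keep the no-contact rule and add SAP text for follow-up survey outcomes.

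1. For between-arm analyses, weight responders by the inverse of their probability of response, modelled by arm from variables available for the whole cohort: pre-trial missed visits, last viral load, age, sex, clinic and baseline survey score. Take the adolescents originally enrolled as the denominator; a replacement under protocol 7.2 does not stand in for a missing response.
2. Report the weighted beside the unweighted result, with a bounds or sensitivity analysis for the non-retained.
3. For mediation, relate the month-6 mediator only to retention after month 6, with the same weights, because the month-6 survey falls under the same rule. The dedicated satisfaction survey is scheduled for month 12 in intervention sites only, so satisfaction can enter this way only if the six-monthly survey records it in both arms.
4. Reconcile protocol 7.3 and 8.1 on whether the phone mode may be used for adolescents who have missed appointments.

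The cost is analysis text and programming, with no new contact, provided that survey and EMR records can be joined for each adolescent. Weighting loses some precision. It also assumes that response is missing at random given the listed variables, which the sensitivity analysis is there to probe.

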8 STUDY ASSESSMENTS AND PROCEDURES

8.1 ENDPOINT AND OTHER NON-SAFETY ASSESSMENTS

Intervention development workshop

The intervention development workshop will be led by study team members. Workshop material will be summarized and sent to participants prior to the workshop. Materials will include literature on the use of risk assessment tools, information on the risk tool from the formative phase of the study, proposed core elements of the risk tool, differentiated care services, best practices for adolescent care, national guidelines on HIV care, flow maps of existing services in clinics in the catchment area and proposed framework for stepped care levels including sample intervention tables. The workshop will begin with a review of all material shared before the workshop. Next, the risk prediction tool will be introduced and discussed in detail in small groups including performance, strengths, weaknesses, and proposed categories. HCWs will be encouraged to think about how the tool would work in their work setting, while incorporating the views of stakeholders. A framework of proposed intervention steps with different levels of care with increasing intensity will be presented. HCWs will discuss what interventions would work at the different levels of care, keeping in mind current practices in the facilities. HCWs will be encouraged to be participatory and as practical as possible, and to develop the most inclusive and simplest interventions that would work in the largest number of facilities in Kenya. Small working groups will present their discussions to the larger group, and the large group will work to come to consensus on a draft tool. The tool will continue to be refined after the workshop, incorporating the views and feedback of all stakeholders present. Selected workshop members will be contacted to review the refined tool after the workshop. The study will provide reimbursement for transportation costs, accommodation and meals during the workshop and provide a per-diem allowance equal to current rates used by organizations or facilities where the HCWs work.

Data Collection Procedures:

Adapted from NIH Behavioral and Social Intervention Clinical Trial Protocol Template v3.0 - 20180827

Small and large group discussions during the workshop will be audio recorded. Notes will be taken during discussions, and audio recordings will be transcribed as needed for team review. Prior to the intervention development workshop, HCWs will complete a short demographic form to collect socio-demographic information. Neither the transcribed notes from the workshop or transcripts will include any personal identifiers other than the participant's first name. Collected transcript data will be de-identified. The audio recordings of discussions will be destroyed after study participation and data analysis has been completed and no later than 6 years after the workshop took place. Audio files and English transcripts will be uploaded to a password protected secure website for back-up. A qualitative software program (ex: ATLAS.ti or Dedoose) will be used for data management and analysis.

Listed below are all the required procedures for the intervention development workshop

- 1) Invitation to participate in workshop
- 2) Collect locator information (phone number) and schedule meeting dates
- 3) Provide a copy of the materials to review prior to the meeting
- 4) Complete demographic surveys
- 5) Present results of qualitative work
- 6) Present the risk prediction tool
- 7) Discussion on how to use the risk tool
- 8) Present outline for proposed DiSC intervention
- 9) Group discussion on DiSC intervention components
- 10) Small group discussions to develop and refine steps in care
- 11) Whole group presentations with iterative refinement
- 12) Presentation of refined tool and risk categories
- 13) Post workshop review of refined tool

Intervention optimization (pilot)

HCWs and AYA in participating sites will consent to participate in the pilot phase which includes intervention administration, twice-monthly intervention adaptation meetings, as well as implementation surveys. At the start of the pilot, HCWs will complete a short demographic form to collect socio-demographic information. HCWs will be introduced to the adapted intervention materials, trained on how to use them, and encouraged to make small adaptations and changes to the way they implement the intervention throughout the pilot period. If a new HCW enters the facility during the pilot, they will also be trained on the intervention materials and have socio-demographic information collected. An implementation/adaptation log will be used to track changes in implementation and HCWs will participate in twice-monthly planning and feedback meetings. Meetings will be audio recorded and transcribed when necessary. Transcripts will not include HCW names. Routinely collected data at the facility, such as the number of adolescents attending and the number of adolescents exposed to the intervention, will be collected to monitor implementation outcomes of adoption and reach. Following the pilot period, HCWs from clinics who participated in the pilot will take part in individual in-depth interviews (IDIs) or focus group discussions (FGDs) to share their suggestions for optimizing the intervention based on their pilot experience. IDIs and FGDs will be audio recorded and will be transcribed verbatim. Transcripts and notes from twice-monthly meetings will be analyzed to identify themes related to how to revise intervention materials and implementation. After the pilot phase, the tool will be further refined with input from selected members who participated in the intervention development workshops prior to use in the RCT phase.

Adapted from NIH Behavioral and Social Intervention Clinical Trial Protocol Template v3.0 - 20180827

Cluster RCT

Intervention details, administration and assessments are described in the sections above (see section 6.1 and 6.2).

Program records: We will abstract ALHIV medical record data at baseline and regular intervals throughout the study. Data from all adolescents with at least 1 clinic record within the 12-month period prior to the first data abstraction date will be included. Data will be abstracted at the facility or at the office of the technical partner that supports the EMR system at the facility. The EMR system captures data on client anthropometric measures, demographics, HIV testing history, family members, clinical history, ART adherence data, laboratory data, CD4 count, transfers, and discontinuations. Routine viral load testing (done 6 months after ART initiation, then annually) will be abstracted from the EMR, if available, or NASCOP's laboratory database. If EMR data is unavailable, paper medical records will be abstracted using mobile REDCap which enables automatic upload of data to a secure, password-protected study server.

Adolescent behavioral surveys: Adolescent surveys will include questions on socio-demographics, health care use, stigma, sexual behavior, psychosocial support, mental health, personal health knowledge, HIV disclosure and medication adherence. Surveys will be administered every 6 months either in-person or over phone by a trained study staff. Survey visits will coincide with clinic visits as much as possible.

Caregiver behavioral surveys: Caregiver surveys will include questions on socio-demographics and family, caregiver roles, HIV disclosure, HIV care experience, disclosure, social support, mental health, HIV testing and awareness, personal health and HIV experience, HIV stigma, ART knowledge and adherence. Surveys will be administered every 12 months either in-person or over phone by a trained study staff. Survey visits will coincide with clinic visits as much as possible.

Data on health services and implementation outcomes will be collected as previously described (see section 6.2).

To track implementation, the following surveys will be conducted:

Facility surveys: Facility managers will complete baseline and annual facility surveys to understand baseline resource capacity to implement future interventions and modifiable and non-modifiable health system factors. Variables will include availability of youth-friendly services, management and referral systems, and differentiated care services available.

HCW surveys and FGDs/IDIs: Surveys with all HCWs at intervention and control sites who are willing to participate will be conducted at baseline and annually on demographic information, including training history and experience providing HIV care. HCWs at intervention sites will also complete an organizational readiness for change survey after training on the intervention, but prior to implementation at their clinic, and will participate in twice-monthly planning and feedback meetings during the first 6 months of implementation. We will conduct surveys, FGDs, and IDIs with HCWs in intervention sites at 6 months post-intervention implementation and at the end of the trial to evaluate barriers and facilitators of intervention implementation, overall implementation outcome measures using the Reach, Effectiveness, Adoption, Implementation and Maintenance (RE-AIM) framework as well as costs. Cost data will be collected from HCW or policy makers in adolescent health, published literature and government data. FGDs and IDIs with HCWs will

Adapted from NIH Behavioral and Social Intervention Clinical Trial Protocol Template v3.0 - 20180827

include a purposeful sample of those exposed to the intervention, stratified by clinic performance level during intervention implementation, cadre of HCW, and involvement in implementation. Exit surveys with HCWs at implementation sites will be conducted to determine experience with the DiSC intervention and barriers and facilitators for intervention utilization. Example validated tools that may be used to inform the surveys and measure each of the implementation outcomes include:

- Determinants of DiSC intervention feasibility and acceptability classified using the Consolidated Framework for Implementation Research (CFIR)
- Intervention adaptation classified according to the framework for reporting adaptations and modifications to evidence-based interventions (FRAME)
- Reach, Acceptability and Feasibility, measured by the Applied Mental Health Research (AMHR) validated implementation science measure[72]
- Adoption, measured using a 17-item validated survey to characterize intervention characteristics and likelihood of adoption[73]
- Implementation, measured using surveys to assess enthusiasm, self-efficacy and preparedness[74]
- Maintenance, measured using the Program Sustainability Assessment Tool (PSAT)

HCW implementation logs: These will be collected weekly and combined with information collected in annual HCW surveys to understand intervention and implementation processes in real time and service efficiency outcomes. We will specifically evaluate the percent of HCWs using the intervention, percent of adolescents in each step, percent of adolescents assigned to correct step, and percent of adolescents ‘adherent’ to services in each step. We will also collect basic information on numbers of adolescents attending clinic each week, and the number exposed to the intervention. In control sites, we will collect information on classification of adolescents as stable/unstable and offer for differentiated services.

ALHIV and caregiver satisfaction surveys: Surveys will be given to a random sample of adolescents and caregivers in intervention sites at the end of the study to evaluate satisfaction with their care.

ALHIV FGDs/IDIs: We will conduct FGDs/IDIs with adolescents in intervention sites at the end of the intervention period to determine acceptability, feasibility and satisfaction with the intervention. FGD/IDI participants will be purposively selected from adolescents in intervention clinics. We will conduct FGDs/IDIs with up to 50 people per facility.

The table below summarizes study outcomes and definitions

Summary of outcomes and definitions

Aims	Outcome type	Outcome	Definition
Aim 1	Primary	Final optimized DiSC intervention	Modified DiSC intervention with input from workshop and pilot phase
	Secondary	DiSC intervention feasibility	Suitability for everyday use and practicality

Adapted from NIH Behavioral and Social Intervention Clinical Trial Protocol Template v3.0 - 20180827

		DiSC intervention acceptability	HCW satisfaction with the intervention
		DiSC intervention adaptation and fidelity	The degree with which the intervention is modified and implemented as planned
Aim 2	Primary	Retention in care	>30 days late for a scheduled visit at 6-month intervals
	Secondary	ART adherence	Proportion of days on ART based on last dispense date
		Viral suppression	<50 copies per milliliter and a second analysis using greater than lower limit of detection
		Co-factors of retention and viral suppression	School drop-out, relationships, depressive symptoms, substance use, social support, and satisfaction with care
		ALHIV self-efficacy	Self-efficacy scales from standard questionnaires
		Health service efficiency	Client wait time
		Costs	Direct and indirect costs of the intervention
		Differentiated care process	% of ALHIV correctly identified as stable or unstable
	Implementation outcomes	Intervention feasibility	Suitability for everyday use and practicality
		Intervention acceptability	HCW and ALHIV satisfaction with the intervention
		Intervention adaptation and fidelity	The degree with which the intervention is modified and implemented as planned
		Intervention adoption	The initial decision to take up a new intervention
		Intervention reach	The integration of the practice within the clinic

		Intervention maintenance	The longer-term ability to sustain or maintain intervention implementation
--	--	--------------------------	--

